## 2.1 Primary Endpoint

This is a randomised two group pilot study comparing;

- 1) xenon inhalation for 18 hours in combination with whole body cooling to 33.5 °C for 3 days, to
- 2) the established treatment of cooling the body down to 33.5 °C for 3 days.

Reference:	CH
Issue:	2
Revision:	3
Issue Date:	1 May 2013
Page	13 of 49

This will be applied in term newborn babies who display signs indicating moderate or severe brain injury following poor condition at birth.

Our hypothesis is that we may observe an enhanced neuroprotective effect of the xenon-cooling combination over cooling alone assessed initially by early outcome predictors. This will allow us to perform power calculations for a much larger neurological outcomes study of otherwise similar design. We have tested a combination of our early predictors (using our TOBY registry cooling data in 80 infants) against Bailey outcome at 18 months and found they have a positive predictive value of 94% in cooled infants

#### **Early predictors of outcome**

#### **For the main analysis we will use**

Time to recovery after birth of a normal aEEG [1]

MRI scan before 14 days of life [33, 2]

Peak LDH value within 72h of life [4, 34]

We will also collect data on:

Plasma glucose at birth (in cord blood)

Age in hours after birth when plasma lactate has fallen to 5mmol/L

Different inotropic drugs needed and the total duration in hours of any inotropic support

Number of anticonvulsants given

Amount and duration of sedation (e.g.morphine)

Age at full oral feeds (breast or bottle or tube)

Neonatal hearing screening result before 14 days of life

Clinical examination at birth, at 7 days of age and at discharge including weight and head circumference

Neurodevelopmental follow up is a part of the routine follow up of infants with HIE, Bayley examination at 18 months of age.

Disability will be defined as any of:

Bayley II mental developmental scale (MDI) score less than 70.

Bayley II motor development scale (PDI) score less than 70. MDI and PDI will also be calculated as DQ, developmental score as this allows a larger range of score for those functioning at a low level [35]. Bilateral cortical visual impairments Hearing loss needing amplification > 40 DB.

In addition any Adverse Events will be recorded and criteria have been devised for stopping the study early if necessary. This includes a Data Review Panel to review data when 4 xenon infants have undergone xenon treatment.

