## Protocol Summary

Title	XENON AND COOLING THERAPY IN BABIES AT HIGH RISK OF BRAIN INJURY FOLLOWING POOR CONDITION AT BIRTH: RANDOMISED PILOT STUDY (COOLXENON2 STUDY)
Investigators	[name] (Chief Investigator) e-mail: [contact] Mob: [name] [name] (Co-Investigator) e-mail: [contact] Mob: [name] [name] (Co-Investigator) e-mail: [contact] Mob: [name] [name] (Co-Investigator) [name] (Co-Investigator) [name] (Co-Investigator) [name] (Co-Investigator) [name] (Co-Investigator) [name] (Co-Investigator) [name] (Co-investigator)
Study Centre	St Michael's Hospital [name]
Test Article	Xenon Neonatal Breathing Device
Objectives	
Primary Objective: This is a randomised two group pilot study comparing:
 
 
i) xenon inhalation for 18 hours in combination with whole body cooling to 33.5 °C for 3 days, to
 
ii) the established treatment of cooling the body down to 33.5 °C for 3 days.
 
 
This will be applied in term newborn babies who are at moderate or high risk of brain injury following poor condition around the time of birth.
 
Our hypothesis is that during the first 2 weeks after birth using a combination of validated (in our own and others cohorts) early predictors of outcome we may observe an enhanced neuroprotective effect of the xenon-cooling combination over cooling alone and this will allow us to perform power calculations for a larger definitive neurological outcomes study of otherwise similar design.
 
Outcome predictors are based on a combination of:
 
 
1) Time in hours after birth when background activity as recorded by amplitude integrated EEG (aEEG: from single channel EEG) [1] and
 

Reference:	CH
Issue:	2
Revision:	3
Issue Date:	1 May 2013
Page	4 of 49

onset of sleep wave cycling (SWC). Time to Normal trace and SWC are both very good (PPV>90%) outcome predictors  
 2) MRI before 2 weeks of age (T1W and T2W) has a PPV of 84% in cooled infants in the TOBY trial in which we were a major recruiting centre [2] Resistance Index (RI) was not a definite predictor for cooled infants [3]). We will do the examination but not use it in the prediction. Peak value of Lactate Dehydrogenase within the first 72h of life [4, and [name] M 2012 submitted ].

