#### **2.2 Secondary Endpoint**

A series of variables that are among the most relevant for evaluation of safety (see endpoints below) were examined closely in the previous 14 baby feasibility/safety study. We will continue to routinely monitor and record the same set of physiological variables in the proposed study, for a subset of data for a longer time period until after rewarming.

- Endpoint 1 – defined as *Mechanical ventilation and gas exchange parameters*
  - The following variables will be measured before (from start cooling), during and after xenon administration (for 12h or until 12h after end of cooling hours pending which variable):Transcutaneous oxygen saturation, end-tidal carbon dioxide concentration, blood gas data, mechanical ventilation requirements (rate, peak inspiratory pressure, inspiratory time, PEEP settings),FiO2. Average percentage xenon in inspired gas mixture (when applicable). Tracheal tube cuff pressure.
- Endpoint 2 – defined as *Haemodynamic parameters*

Reference:	CH
Issue:	2
Revision:	3
Issue Date:	1 May 2013
Page	14 of 49

- The following variables will be measured before, during and after xenon administration: Systolic, mean and diastolic arterial pressures, Heart rate.
- Endpoint 3 – defined as *Inotropic drug requirements*
  - These (drug, dose and duration) will be recorded before, during and after xenon administration until 12h after end of cooling.
- Endpoint 4 – defined as *Marker of myocardial impairment/insult*  
The following will be recorded before and after xenon administration: Plasma levels Troponin T (marker of myocardial cell death) recorded before and after xenon administration until 12h after end of cooling:
  - Endpoint 5 – defined as timecourse and peak value of *Markers of hepatic impairment*
    - These will be recorded before and after xenon administration until 12h after end of cooling: [Alanine aminotransferase , Alkaline phosphatase and Lactate Dehydrogenase]
  - Endpoint 6 – defined as timecourse and peak value of *Markers of renal impairment*
    - These will be recorded before, during and after xenon administration until 12h after end of cooling: oliguria is defined as [urine output < 1 ml/kg/h] from age > 24h, raised creatinine > 100 at > 24h of age.
  - Endpoint 7 – defined as *Evidence of infection*
    - These will be recorded: culture proven, need for antibiotics for 5 or more days, raised CRP occurring within 24h or later.

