1. The dose (fraction of xenon in breathing gas) planned for each patient in the xenon+cooling group will be 50%. It will be applied for 18 hours. It will be commenced as soon as is practicable but no later than 5h after birth once all the entry criteria / consent requirements have been met.
2. If a baby is being retrieved from another local hospital to the study centre (Bristol) using the existing Bristol-provided retrieval team and ambulance, AND they have been consented and randomised to receive xenon AND if it is deemed probable that the delay between birth and the start of xenon in Bristol would exceed an interval of 5 hours, then if logically possible an assigned research team member will accompany or meet the retrieval team and commence xenon delivery at the local hospital or during the return transfer of the baby to Bristol.
- 3) Full data sets will be acquired in two groups of 16 patients. The mortality rate in the patients referred for cooling to Bristol is ~25%.
- 4) Cooling will be for 72 hours using the clinically chosen cooling device in both groups, as is current standard practice for cooling.

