#### **Group size calculation**

Sixteen babies will be recruited into each group (cooling+xenon vs cooling alone) at random. The cooling will be applied as standard treatment if cooling criteria are met. Addition of xenon in combination with this underlying cooling will take place in the group randomised to receive cooling + xenon.

For pilot studies of this type the recommendation is a sample size of 12 per group. The justifications for this sample size are based on

- i) Feasibility – allows convenient block sizes, for example our intention for a data review committee to review data sets at block intervals of 4 neonates.
- ii) Precision about the mean – little additional precision to be gained by having a larger group size than 12 [44].
- iii) Precision about the variance – little additional precision to be gained by having a larger group size than 12 [44].

Reference [44] presented in full in Appendix 10.

The first 15 neonates were recruited in a period where the xenon ambulance transfer system was not ready for use. The clinical staff employed to recruit and deliver the xenon in the ambulance needed time to gain experience using the system before using it independently away from the base hospital without the supervision of [name]. This has led to a similar number of babies which we failed to recruit (due to the time limitation) as the number recruited to

Reference:	CH
Issue:	2
Revision:	3
Issue Date:	1 May 2013
Page	25 of 49

xenon. We therefore wish to recruit a further 8 babies to assess the feasibility to recruit, more reliably, consecutive babies fulfilling the entry criteria within the confines of the protocol

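### Peak LDH counted from birth can include values drawn before xenon; adjust the between-arm difference for the first LDH and keep the 72-hour peak for the predictor and historical comparisons

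*Protocol*

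**What the plan says.** Protocol Section 2.1, under the early predictors of outcome, introduces three markers with "For the main analysis we will use". They are time to a normal aEEG, MRI before 14 days, and "Peak LDH value within 72h of life". The Protocol Summary gives the same window: "Peak value of Lactate Dehydrogenase within the first 72h of life". Sections 3.2 and 7.5.4 repeat it.

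On the timing of xenon, Section 3.1 (management of the xenon+cooling group, item 1) says: "It will be commenced as soon as is practicable but no later than 5h after birth".

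On LDH sampling, Section 2.2 lists LDH under Endpoint 5, which is "defined as timecourse and peak value of" the hepatic markers: "These will be recorded before and after xenon administration until 12h after end of cooling: [Alanine aminotransferase , Alkaline phosphatase and Lactate Dehydrogenase".

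Section 9.1 limits the presentation to descriptive statistics but says that differences between the groups will be estimated. Section 2.0 intends the early predictors to support power calculations for a larger trial. No section restricts the peak to samples taken after randomisation or after xenon starts, and none uses the pre-xenon LDH as a baseline.

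**The concern.** One definition serves two purposes. As a predictor of outcome, a peak counted from birth is sensible, because the severity of the insult is part of what it should capture. As a measure of what xenon adds to cooling, it is less suitable. If an infant's highest LDH was drawn before xenon began, the recorded value would have been the same in either arm.

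Two things are at stake. First, such infants add values that cannot respond to treatment, which pulls the between-arm difference towards zero by an unknown amount. Second, with 16 infants per arm, chance differences in the severity of the birth insult can be sizeable, and they pass into the LDH difference. That difference is among the results meant to inform the size of the definitive trial.

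**Working it through.** **Is there a figure in the Protocol to reproduce?** No. It gives no LDH standard deviation, effect size, sampling frequency or time of peak. The results below are therefore in SD units, and assumptions are marked.

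**Step 1. Can a pre-xenon value be the peak?**
- The window is 0 to 72 h of age (Section 2.1).
- Xenon starts at 5 h of age at the latest (Section 3.1), so up to 5/72 = 6.9% of the window precedes it.
- LDH is recorded before xenon (Section 2.2, Endpoint 5).
- Nothing removes that value from the peak.

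So it can be. The 6.9% is a share of hours, not of peaks. The recorded peak is the highest of the samples drawn, and the LDH schedule is not stated. Endpoint 5 mentions sampling before and after xenon, while Endpoint 6 also mentions sampling during it. The share of peaks that fall early cannot be derived from the Protocol.

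**Step 2. How large can chance imbalance be?** Section 3.3 sets the group size: "Sixteen babies will be recruited into each group (cooling+xenon vs cooling alone) at random".
- Standard error of a between-arm difference in first LDH = SD × sqrt(2/16) = 0.354 SD.
- 95% range = ±1.96 × 0.354 = ±0.69 SD.
- Probability that the difference exceeds 0.5 SD in either direction = 2 × [1 − Φ(0.5/0.354)] = 15.7%.
- If the first and peak values correlate at r (equal SDs assumed), a first-value difference of 0.5 SD shifts the expected peak difference by r × 0.5 SD: 0.25 SD at r = 0.5 and 0.35 SD at r = 0.7.

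**Step 3. What does adjustment gain?**
- Unadjusted 95% half-width = t(30) × sqrt(2/16) = 2.042 × 0.354 = 0.72 SD.
- Adjusted half-width ≈ 0.72 × sqrt(1 − r²), ignoring the one degree of freedom spent.
- r = 0.5 (assumed): 0.72 × 0.866 = 0.63 SD (0.625 before rounding).
- r = 0.7 (assumed): 0.72 × 0.714 = 0.52 SD (0.516 before rounding).

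This is the ordinary gain from using a baseline covariate. It measures what the remedy offers, not the harm done by the birth-based window.

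**Step 4. Would a later window alone suffice?** No. Values after randomisation are also expected to correlate with the first value. A peak restricted to later samples removes values that treatment could not reach, but it still carries the chance imbalance of Step 2. Only adjustment deals with that.

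**The case against.** The strongest reply is that the window is deliberate. Sections 3.2 and 7.5.4 give peak LDH before 72 h a positive predictive value of 80% in cooled babies. Section 2.0 compares LDH with earlier cohorts, and Section 9.1 makes comparison with historical controls the second stated purpose of the pilot. A peak counted from randomisation has neither a predictive value nor a historical range in the Protocol. This stands, and it is why the 72-hour peak should be kept.

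It is also fair that little hangs on the LDH difference. The study is descriptive, disclaims power to test outcome, puts feasibility of early recruitment first, and uses LDH alongside two other markers. No test or decision rule is invalidated. What remains is the intended use of the predictors in later power calculations.

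Baseline adjustment could be left to a statistical analysis plan, which is not at hand. The Protocol does, however, fix this marker's window itself and assigns no role to the pre-xenon value, so one sentence on its use is worth adding.

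Finally, a usable baseline in controls is not guaranteed. Endpoint 5 times LDH only relative to xenon, which controls do not receive, and Section 3.1 estimates that more than 90% of infants are born elsewhere. That stands as a condition on the remedy.

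**Conclusion.** The point holds as a modest one. A pre-xenon LDH lies inside the window of a main marker, can be its peak, and has no stated role as a baseline. The between-arm difference can therefore include values that treatment could not affect, and it carries chance imbalance in the birth insult.

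A reader might infer that a stated fraction of any xenon effect, such as a quarter or a half, is lost. The Protocol does not support this, because it gives neither the timing of the LDH peak nor the sampling frequency. Purely as illustration, take the peak as the larger of a pre-xenon value (SD 1) and a later value (true effect 0.5 SD, residual SD 0.75). The share of the effect retained is then 95%, 63% or 37% if 2%, 25% or 50% of control peaks are early. The answer depends entirely on an input that the Protocol does not supply.

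A reader might also infer bias. Randomisation makes the imbalance a matter of chance, and it affects any severity-related marker in a trial of this size.

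The quantifiable benefit is precision: a half-width of 0.72 SD falling to 0.63–0.52 SD. It rests on an assumed correlation of 0.5–0.7 and on a first LDH being available in both arms.

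**What to change.** Leave peak LDH to 72 h of life as it is for prediction and for comparison with historical infants. Add to Section 9.1, or to the analysis plan, wording to this effect:

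- The between-arm difference in peak LDH is estimated with adjustment for the first LDH, drawn before randomisation in controls and before randomisation or xenon in the xenon arm. It is given with its 95% interval.
- The first LDH and its age at sampling are summarised by arm.
- A peak restricted to samples after randomisation may be added as a supplementary summary. It does not replace the adjustment.
- Infants with no qualifying first LDH are counted by arm and handled by a rule written before the data are examined.

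The adjusted estimate is an estimated difference, so it fits the descriptive aim. The cost is small: analysis wording, plus confirmation that a first LDH timed to randomisation exists in controls. For infants already recruited this means checking the samples on record; the baseline cannot be assumed to be present in every case.

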#### **2.2 Secondary Endpoint**

A series of variables that are among the most relevant for evaluation of safety (see endpoints below) were examined closely in the previous 14 baby feasibility/safety study. We will continue to routinely monitor and record the same set of physiological variables in the proposed study, for a subset of data for a longer time period until after rewarming.

- Endpoint 1 – defined as *Mechanical ventilation and gas exchange parameters*
  - The following variables will be measured before (from start cooling), during and after xenon administration (for 12h or until 12h after end of cooling hours pending which variable):Transcutaneous oxygen saturation, end-tidal carbon dioxide concentration, blood gas data, mechanical ventilation requirements (rate, peak inspiratory pressure, inspiratory time, PEEP settings),FiO2. Average percentage xenon in inspired gas mixture (when applicable). Tracheal tube cuff pressure.
- Endpoint 2 – defined as *Haemodynamic parameters*

Reference:	CH
Issue:	2
Revision:	3
Issue Date:	1 May 2013
Page	14 of 49

- The following variables will be measured before, during and after xenon administration: Systolic, mean and diastolic arterial pressures, Heart rate.
- Endpoint 3 – defined as *Inotropic drug requirements*
  - These (drug, dose and duration) will be recorded before, during and after xenon administration until 12h after end of cooling.
- Endpoint 4 – defined as *Marker of myocardial impairment/insult*  
The following will be recorded before and after xenon administration: Plasma levels Troponin T (marker of myocardial cell death) recorded before and after xenon administration until 12h after end of cooling:
  - Endpoint 5 – defined as timecourse and peak value of *Markers of hepatic impairment*
    - These will be recorded before and after xenon administration until 12h after end of cooling: [Alanine aminotransferase , Alkaline phosphatase and Lactate Dehydrogenase]
  - Endpoint 6 – defined as timecourse and peak value of *Markers of renal impairment*
    - These will be recorded before, during and after xenon administration until 12h after end of cooling: oliguria is defined as [urine output < 1 ml/kg/h] from age > 24h, raised creatinine > 100 at > 24h of age.
  - Endpoint 7 – defined as *Evidence of infection*
    - These will be recorded: culture proven, need for antibiotics for 5 or more days, raised CRP occurring within 24h or later.
  - Endpoint 8 – defined as *Length of hospital stay including duration of stay in local hospital after discharge from St Michaels hospital*
    - This will be recorded
  - Endpoint 9 – defined as *age when full oral feeding was achieved by breast or bottle or tube*
    - This will be recorded
  - Endpoint 10 – defined as *Haematology measurements*
    - These will be recorded before and after xenon administration (these are routinely recorded 24 hrly): Coagulopathy [INR > 2 and/or APTT > 50]. Full blood count.
  - Endpoint 11 – defined as *Serum chemistry measurements*
    - These will be recorded before and after xenon administration: Serum sodium, potassium, chloride, magnesium, phosphate, calcium, (urea, creatinine as above), glucose, (liver enzymes as above), bilirubin, albumin. Drug levels may be analysed on clinical indication (Gentamicin levels, Phenobarbital levels).
  - Endpoint 12 – defined as aEEG background pattern and *Evidence of seizures*
    - These will be recorded before, during and after xenon administration until 12h after end of cooling: Evidence from continuous aEEG/EEG recording and any anticonvulsant treatments given.

### 3.0 Study Design

This is a single centre prospective randomised clinical pilot study.

Reference:	CH
Issue:	2
Revision:	3
Issue Date:	1 May 2013
Page	15 of 49

**Eligibility**  
 Meet inclusion and exclusion criteria  
 This includes  
 ≥36.0 weeks gestational age  
 Expectation of being able to start cooling at ≤3h age and, if required  
 Xe at ≤5h age.

**Explanation of study to parent**  
 If eligible, parent(s) given 1 page, short version information leaflet.  
 Leaflet given by member of the team or local trained staff in referring hospital.  
 Verbal explanation as soon as possible, given by one of  

- Named Physician (local or on research team)
- Trained nurse such as an advanced nurse practitioner
- Parents also able to speak on telephone with member of treatment team and given opportunity to speak to members of the retrieval team.

 \*More detailed information sheet given to parents after first conversation or at earliest suitable time.

**Who can consent?**  

- Either parent if married
- Mother only if not married, provided she is awake and understanding
- If not married and mother not awake/understanding and the biological father does currently not have legal parental responsibility he can assent for the trial until the mother is awake/understanding and able to decide on consent.

**Written consent, obtained by**  

- Named Physician (local or on research team)
- Trained staff on transport team can also take consent for the study.
- Consent can also be taken from mother over the telephone by named physician on research team if for example she cannot be immediately moved after delivery/Caesarian Section, followed by her written consent as soon as possible.

 \*Parents can withdraw child at any time.

**Randomisation**  
 Cooling-only and cooling + xenon groups.

**Cooling group**  
 Sedate, mechanically ventilate, cool.  
 If retrieved baby, cooling commenced prior to transfer to Bristol (passive or active).

**Cooling + xenon group**  
 Sedate, mechanically ventilate for cooling.  
 Replace tracheal tube with cuffed of same or 0.5mm smaller size.  
 Inflate cuff until seal just achieved.  
 Commence cooling as in cooling-only group.  
 Commence 50% xenon in breathing gas, maintain for 18h, (cooling continuing to total of 72h).

Reference:	CH
Issue:	2
Revision:	3
Issue Date:	1 May 2013
Page	16 of 49

